2.5.2 Part 2: Primary and Key Secondary Efficacy Objectives Estimands

The estimands corresponding to the Part 2 RWP primary and key secondary objectives and endpoints are described in [Table 6](#) and [Table 7](#), respectively.

Table 6: Estimand for the RWP Part 2 Primary Objective

Objective	To evaluate efficacy of SYNB1934v1 versus placebo in the responder population
A. Population	The population is the RWP responder full analysis set (defined in Section 3.5) characterized by the inclusion/exclusion criteria provided in Section 4.2 of the study protocol.
B. Variable	Continuous variable: Change from RWP baseline to Week 4 in blood Phe level

C. Intercurrent events	
• Treatment discontinuation: consistent with a treatment-policy strategy, treatment discontinuation will not be considered (i.e., all observed data will be used regardless of treatment discontinuation).• Antibiotic use: consistent with a treatment-policy strategy, antibiotic use will not be considered (i.e., all observed data will be used regardless of antibiotic use).• Prohibited medication use: consistent with a treatment-policy strategy, prohibited medication use will not be considered (i.e., all observed data will be used regardless of prohibited medication use).
D. Population-level summary	The population-level summary is the least-squares means and difference in the change from baseline to Week 4 in blood Phe levels between the SYNB1934v1 and placebo treatment groups. An MMRM using an observed case approach is being applied. The post-baseline blood Phe levels at Weeks 1, 3, and 4 will be used. The MMRM model is described in Section 3.14.2.1 .

MMRM = mixed model with repeated measures; Phe = phenylalanine; RWP = randomized withdrawal period.

Table 7: Estimands for the RWP Part 2 Key Secondary Objectives

Objective	To evaluate the efficacy of SYNB1934v1 versus placebo in the responder population with regard to the percent change from DEP baseline in blood Phe level
A. Population	The population is the RWP responder full analysis set (defined in Section 3.5) characterized by the inclusion/exclusion criteria provided in Section 4.2 of the study protocol.
B. Variable	Continuous variable: Percent change from DEP baseline to Week 4 in blood Phe level.

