3.5 Analysis Populations

Analysis populations will be defined for each of the 3 parts of the study (DEP, RWP, and OLE).

Full analysis set (FAS): The full analysis sets are based on the intention-to-treat principle. The DEP FAS includes all participants enrolled in the DEP who take at least one dose of DEP study medication.

The RWP FAS is defined as all participants randomized into the RWP who take at least one dose of RWP study medication. Additionally:

- The responder RWP FAS is defined as participants in the RWP FAS who are responders
- The nonresponder RWP FAS is defined as participants in the RWP FAS who are nonresponders.

A responder is defined as a participant who achieves a $\geq 20\%$ reduction in blood Phe level compared to DEP baseline on SYNB1934v1.

The responder RWP FAS will be the primary efficacy analysis population for the RWP. Analyses on the RWP FAS will be performed according to the randomized treatment group.

In the event that, based on the interim analysis results utilizing the criteria provided in [Table 10](#), the DMC recommends dropping either the 1×10^{12} or the 1×10^{12} and 6×10^{11} doses the following will occur:

- The participants in the DEP who have an iTD corresponding to a dropped dose will go directly into the OLE part of the study (i.e., as opposed to being randomized into the RWP).
- The RWP FAS, responder RWP FAS, and nonresponder RWP FAS, will exclude all participants whose iTD dose level was dropped.

These participants who are excluded from the RWP FAS will be summarized separately.

Safety analysis set (SAS): For each of the 3 study parts, the SAS will include all participants who received any amount of IMP in the corresponding study part with treatment assignment based on the treatment received.

For the RWP the safety analyses will be presented for the RWP SAS overall as well as by responder/nonresponder subgroups. Similarly, the OLE safety analyses will be presented for the OLE SAS overall as well as by responder/nonresponder subgroups.

A participant will be considered receiving treatment if the eCRF question “did the patient receive any study drug doses” is answered “Yes” and there is a corresponding non-missing date.

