3.14.2 Part 2: RWP

The efficacy analyses for the RWP will be based on the responder RWP FAS (defined in [Section 3.5](#)) unless explicitly stated otherwise.

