3.14.2.4 Key Secondary Efficacy Endpoint Analyses

The key secondary efficacy endpoint analyses for the RWP are provided below. These analyses will be performed on the responder RWP FAS.

- ***Percent change from DEP baseline in blood Phe level at Week 4***

The percent change from DEP baseline to Week 4 in blood Phe level, will be analyzed using an MMRM analysis similar to the model described for the RWP primary efficacy analysis ([Section 3.14.2.1](#)), with the dependent variable being the percent change in blood Phe level from DEP baseline, and the DEP baseline blood Phe level as the baseline blood Phe level covariate. This will be an observed-case analysis using the DEP FAS population, missing data will not be imputed. Note that if the MMRM model does not converge, the same methodology as described for the RWP primary efficacy analysis ([Section 3.14.2.1](#)) will be applied.

- ***Change from DEP baseline to Week 4 in blood Phe level***

The change from DEP baseline to Week 4 in blood Phe level, will be analyzed using an MMRM analysis similar to the model described for the RWP primary efficacy analysis ([Section 3.14.2.1](#)), with the dependent variable being the change in blood Phe level from DEP baseline, and the DEP baseline blood Phe level as the baseline blood Phe level covariate. This will be an observed-case analysis using the responder RWP FAS population, missing data will not be imputed. Note that if the MMRM model does not converge, the same methodology as described for the RWP primary efficacy analysis ([Section 3.14.2.1](#)) will be applied.

- ***Blood Phe level $\leq 360 \mu\text{mol/L}$ at Week 4***

The proportion of participants meeting the key secondary endpoint, Blood Phe level $\leq 360 \mu\text{mol/L}$ at Week 4, will be tested between the placebo and SYNB1934v1 treatment groups using a Fisher's Exact test. This will be an observed-case analysis approach using the responder RWP FAS such that if a participant is missing the data needed to determine the endpoint, they will be considered as not having met the endpoint.

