3.14.2.5 Key Secondary Sensitivity and Supplementary Analysis

- The following are the set of sensitivity and supplementary analysis for the RWP Key secondary endpoints:
- ***Percent change from DEP baseline in blood Phe level at Week 4***

- **Imputation of Missing Data:** Multiple imputation methods will be used to impute missing blood Phe data during the RWP. The imputation of missing data analysis will be performed twice, once assuming the data is missing at random (MAR), and also assuming missing not at random (MNAR). The methodology for the multiple imputation and analysis is provided in [Section 3.18.2](#). The analysis model will be the same model as the corresponding key secondary endpoint analysis.
- **Analysis of Covariance:** The percent change from DEP baseline to Week 4 in blood Phe level endpoint will be analyzed using an ANCOVA model. The percent change from DEP baseline to Week 4 in blood Phe level will be the dependent variable, using the average of the duplicate Week 4 blood Phe levels (i.e., if one of the values is missing, the non-missing value will be used). The ANCOVA has treatment as a fixed effect, and DEP baseline Phe is a covariate.
- **RWP PPS Analysis:** The key secondary efficacy MMRM analysis will be performed using the responder RWP PPS analysis set (defined in [Section 3.5](#)).

Excluding Observations after Treatment Discontinuation, Antibiotic use, or Prohibited Medication: The key secondary efficacy endpoint analysis will be performed on the responder RWP FAS using an observed case analysis which excludes observations after the following intercurrent events occur in the RWP: Treatment discontinuation, antibiotic use, prohibited medication use.

- ***Change from DEP baseline to Week 4 in blood Phe level***

- **Imputation of Missing Data:** Multiple imputation methods will be used to impute missing blood Phe data during the RWP. The imputation of missing data analysis will be performed twice, once assuming the data is missing at random (MAR), and also assuming missing not at random (MNAR). The methodology for the multiple imputation and analysis is provided in [Section 3.18.2](#). The analysis model will be the same model as the corresponding key secondary endpoint analysis.

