3.14.2.6 Control of Multiplicity

The overall Type I error rate for the RWP will also be controlled at the [REDACTED] for the primary endpoint (i.e., DEP, and RWP, will each have a 2-sided Type I error rate of [REDACTED]). The control of multiplicity at [REDACTED] within each study part is consistent with this study having 3 parts, with each study part having a distinct set of objectives, endpoints, and analysis populations.

For the RWP, the 3 key secondary endpoints will be tested at the [REDACTED] level using a fixed sequential testing methodology in this order:

- 1) Percent change from DEP baseline to Week 4 in blood Phe level.
- 2) Change from DEP baseline to Week 4 in blood Phe level
- 3) Blood Phe level $\leq 360 \mu\text{mol/mL}$ at Week 4

These key secondary endpoints will be tested following this prespecified order only if the RWP primary efficacy endpoint null hypothesis is rejected. An endpoint analysis will be considered statistically significant if the corresponding test for that analysis and all previous endpoint analyses are statistically significant using a [REDACTED] Type I error rate [REDACTED]

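### Two stray sentences in the SAP's confirmatory RWP rules: the first key secondary names the DEP FAS, and the primary's non-convergence fallback names two outcome scales

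*SAP*

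**What the plan says.** **Population of the first key secondary.** SAP 3.14.2.4 opens with "These analyses will be performed on the responder RWP FAS". The bullet for percent change from DEP baseline at Week 4 then says "This will be an observed-case analysis using the DEP FAS population, missing data will not be imputed". The next bullet, for absolute change from DEP baseline, says "This will be an observed-case analysis using the responder RWP FAS population, missing data will not be imputed". The third, for Phe at or below 360 µmol/L, also names the responder RWP FAS.

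Elsewhere the SAP is consistent. Section 3.14.2 states "The efficacy analyses for the RWP will be based on the responder RWP FAS", though it allows for explicit exceptions. Table 7 gives the estimand for this endpoint as "The population is the RWP responder full analysis set". For a supplementary analysis of the same endpoint, 3.14.2.5 says "The key secondary efficacy endpoint analysis will be performed on the responder RWP FAS using an observed case analysis". Protocol 8.5.2 uses the same population.

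**Gating.** SAP 3.14.2.6 puts percent change first of the three key secondaries and adds: "An endpoint analysis will be considered statistically significant if the corresponding test for that analysis and all previous endpoint analyses are statistically significant".

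**Fallback for the primary.** SAP 3.14.2.1 and Table 6 define the RWP primary as absolute change from RWP baseline to Week 4. If the planned MMRM does not converge, 3.14.2.2 averages the duplicates and refits. It names the outcome three times: change, change, then percent change.

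**The concern.** A confirmatory rule should have only one reading. Here the population of the first gated test, and the outcome of the primary under its fallback, each have two.

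The general default in 3.14.2 does not cleanly settle the population, because it gives way to explicit statements and the stray sentence is one. Taken literally, that sentence would produce a test that does not answer the Table 7 question, and the two later key secondaries depend on that test. In the fallback, percent change from RWP baseline is an exploratory endpoint in SAP 3.14.2.8, so the stray sentence would put an exploratory scale in the primary's place.

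Timing also matters. SAP 2.2.2 gives the CRO's blinded team access to participant-level Phe. Deciding between conflicting sentences late, with outcome data in view, is harder to defend than a dated correction.

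**Working it through.** This is mainly a comparison of texts. The RWP sample size and power are redacted, so there is no figure in the plan to reproduce.

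**1. Population named for percent change from DEP baseline**

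| Place | Population |
|---|---|
| SAP 3.14.2.4, opening sentence | responder RWP FAS |
| SAP 3.14.2.4, percent-change bullet | **DEP FAS** |
| SAP 3.14.2.4, the two sibling bullets | responder RWP FAS |
| SAP 3.14.2, default | responder RWP FAS, exceptions allowed |
| SAP Table 7 | responder RWP FAS |
| SAP 3.14.2.5, analysis excluding data after intercurrent events | responder RWP FAS |
| Protocol 8.5.2 | responder RWP FAS |
| SAP 3.20, list of changes | no change recorded |

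Within 3.14.2.4 the count is three statements to one. The odd sentence appears word for word in the DEP ANCOVA paragraphs of SAP 3.14.1.3 and 3.14.1.5, where it is correct.

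**2. What the literal sentence would do.** The model needs a treatment arm and RWP visits. DEP participants who were never randomised have neither and drop out of an observed-case fit. What remains is everyone with a randomised arm and RWP data, which differs from the intended set in two ways:

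- Nonresponders enter. The protocol synopsis plans on about 50% responders. If that share held among those randomised, the set would be 1/0.5 = 2 times the intended size, and half of it would be nonresponders.
- If a dose is dropped, RWP participants on that dose enter too. SAP 3.5 states "The RWP FAS, responder RWP FAS, and nonresponder RWP FAS, will exclude all participants whose iTD dose level was dropped", while 3.20 says the DEP FAS now keeps them.

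The SAP already analyses both groups separately (3.14.2.8 and 3.14.2.9).

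**3. Why no power effect is claimed.** No planning values are given for this endpoint. As a stand-in, take the primary's inputs from the synopsis (difference 245, SD 247 µmol/L, 1:1, two-sided 0.05) and assume 80% power, since the true figure is redacted. A t-test then needs 17 per arm. Double that to 34, hold the SD at 247, and let nonresponders have a fraction f of the responder effect:

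- Diluted difference = 245 × (0.5 + 0.5f).
- f = 0 gives 122.5 and power of about 52%.
- f = 0.5 gives 183.75 and power of about 86%.

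Power can move either way, so the point rests on the mismatch with the estimand.

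**4. Outcome named in the fallback.** In 3.14.2.2 the count is two for change and one for percent change. The percent-change wording matches the DEP dose-level fallback in 3.14.1.3, where percent change is the right outcome. The two scales are not interchangeable: a change of 245 µmol/L is 245/400 = 61% of an assumed baseline of 400, and 245/1200 = 20% of an assumed baseline of 1200.

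**5. Related slips.** Both continuous key secondaries send non-convergence to 3.14.2.1, which has no such rule. It is in 3.14.2.2, so they inherit the contradictory text. The DEP absolute-change fallback in 3.14.1.5 has the reverse error, calculating percent change and then modelling change.

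**The case against.** The strongest reply is that this is proofreading. The intended population is fixed in many places, two of them with no exception clause (the opening of 3.14.2.4 and Table 7). The stray sentence cannot be applied to the full DEP FAS, and it cannot be followed without breaking the opening sentence of its own section. In 3.14.2.2, a later sentence says the refitted model is otherwise the same and names only the covariance structure as different, which suggests the outcome was not meant to change. The scale conflict arises only on non-convergence, and no bias, type I error inflation or loss of power has been shown.

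Much of this stands, and it limits the severity. It does not remove the point. The sentence about the refitted model explains sameness as the same fixed effects, so it does not settle the outcome scale. Because the default in 3.14.2 allows explicit exceptions, the DEP FAS wording keeps a literal foothold. The SAP's authors have also treated a comparable conflict as worth resolving: 3.20 reconciles the protocol's two testing orders for these same key secondaries.

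**Conclusion.** The concern holds. Both sentences are in the current SAP text and contradict the rest of the plan. The first gives the leading gated key secondary a population that does not match its estimand. The second leaves the primary's fallback with two outcomes.

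The practical size is limited. The intent can be recovered, the first conflict is reached only after the primary succeeds, and the second only if the planned model does not converge. No effect on power or on the estimate is claimed, and the calculations above are illustrations under stated assumptions. That both sentences were carried over from the DEP sections is inferred from matching wording. The conflict stands whatever its origin. It should be corrected, and it does not call the design into question.

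**What to change.** Amend the SAP before RWP unblinding:

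1. In the percent-change bullet of 3.14.2.4, replace DEP FAS with responder RWP FAS.
2. In 3.14.2.2, delete the percent-change sentence and attach its note on averaged Week 1, 3 and 4 values to the preceding sentence on change from baseline.
3. In 3.14.2.4, point the non-convergence rule to 3.14.2.2 and state that each key secondary keeps its own dependent variable and the DEP-baseline covariate. This must accompany item 2. Otherwise the percent-change key secondary would inherit a fallback that names only absolute change.
4. As a minor edit, correct the reverse slip in the DEP absolute-change fallback of 3.14.1.5.

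The cost is a few wording edits, with no new data, participants or analyses.

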3.14.2.5 Key Secondary Sensitivity and Supplementary Analysis

- The following are the set of sensitivity and supplementary analysis for the RWP Key secondary endpoints:
- ***Percent change from DEP baseline in blood Phe level at Week 4***

- **Imputation of Missing Data:** Multiple imputation methods will be used to impute missing blood Phe data during the RWP. The imputation of missing data analysis will be performed twice, once assuming the data is missing at random (MAR), and also assuming missing not at random (MNAR). The methodology for the multiple imputation and analysis is provided in [Section 3.18.2](#). The analysis model will be the same model as the corresponding key secondary endpoint analysis.
- **Analysis of Covariance:** The percent change from DEP baseline to Week 4 in blood Phe level endpoint will be analyzed using an ANCOVA model. The percent change from DEP baseline to Week 4 in blood Phe level will be the dependent variable, using the average of the duplicate Week 4 blood Phe levels (i.e., if one of the values is missing, the non-missing value will be used). The ANCOVA has treatment as a fixed effect, and DEP baseline Phe is a covariate.
- **RWP PPS Analysis:** The key secondary efficacy MMRM analysis will be performed using the responder RWP PPS analysis set (defined in [Section 3.5](#)).

Excluding Observations after Treatment Discontinuation, Antibiotic use, or Prohibited Medication: The key secondary efficacy endpoint analysis will be performed on the responder RWP FAS using an observed case analysis which excludes observations after the following intercurrent events occur in the RWP: Treatment discontinuation, antibiotic use, prohibited medication use.

- ***Change from DEP baseline to Week 4 in blood Phe level***

- **Imputation of Missing Data:** Multiple imputation methods will be used to impute missing blood Phe data during the RWP. The imputation of missing data analysis will be performed twice, once assuming the data is missing at random (MAR), and also assuming missing not at random (MNAR). The methodology for the multiple imputation and analysis is provided in [Section 3.18.2](#). The analysis model will be the same model as the corresponding key secondary endpoint analysis.
- **Analysis of Covariance:** The change from DEP baseline to Week 4 in blood Phe level endpoint will be analyzed using an ANCOVA model. The change from DEP baseline to Week 4 in blood Phe level is the dependent variable, using the average of the duplicate Week 4 blood Phe levels (i.e., if one of the values is missing, the non-missing value will be used). The ANCOVA has treatment as a fixed effect, and DEP baseline Phe is a covariate. This will be an observed-case analysis using the responder RWP FAS population, missing data will not be imputed.
- **RWP PPS Analysis:** The key secondary efficacy MMRM analysis will be performed using the responder RWP PPS analysis set (defined in [Section 3.18.2](#)).
- ***Excluding Observations after Treatment Discontinuation, Antibiotic use, or Prohibited Medication:*** The key secondary efficacy endpoint analysis will be performed on the responder RWP FAS using an observed case analysis which excludes observations after the following intercurrent events occur in the RWP: Treatment discontinuation, antibiotic use, prohibited medication use.

- ***Blood Phe level $\leq 360 \mu\text{mol/L}$ at Week 4***

- **Exact Logistic Regression:** The Blood Phe level $\leq 360 \mu\text{mol/L}$ at Week 4 endpoint will be tested between the placebo and SYNB1934v1 treatment groups using an exact logistic regression with treatment group as a factor and RWP Baseline Blood Phe ($\leq 360 > 360 \mu\text{mol/L}$) as a dichotomous covariate. This will be an observed-case analysis approach using the responder RWP FAS such that if a participant is missing the data needed to determine the endpoint, they will be considered as not having met the endpoint.
- **RWP PPS Analysis:** The Fisher's exact test will be performed using the responder RWP PPS analysis set.
- **Excluding Observations after Treatment Discontinuation, Antibiotic use, or Prohibited Medication:** The Blood Phe level $\leq 360 \mu\text{mol/L}$ at Week 4 endpoint will be tested via Fisher's Exact Test using an observed case analysis which excludes observations after the following intercurrent events occur in the RWP: Treatment discontinuation, antibiotic use, prohibited medication use. This will be an observed-case analysis approach using the responder RWP FAS such that if a participant is missing the data needed to determine the endpoint, they will be considered as not having met the endpoint.

3.14.2.6 Control of Multiplicity

The overall Type I error rate for the RWP will also be controlled at the [REDACTED] for the primary endpoint (i.e., DEP, and RWP, will each have a 2-sided Type I error rate of [REDACTED]). The control of multiplicity at [REDACTED] within each study part is consistent with this study having 3 parts, with each study part having a distinct set of objectives, endpoints, and analysis populations.

For the RWP, the 3 key secondary endpoints will be tested at the [REDACTED] level using a fixed sequential testing methodology in this order:

- 1) Percent change from DEP baseline to Week 4 in blood Phe level.
- 2) Change from DEP baseline to Week 4 in blood Phe level
- 3) Blood Phe level $\leq 360 \mu\text{mol/mL}$ at Week 4

These key secondary endpoints will be tested following this prespecified order only if the RWP primary efficacy endpoint null hypothesis is rejected. An endpoint analysis will be considered statistically significant if the corresponding test for that analysis and all previous endpoint analyses are statistically significant using a [REDACTED] Type I error rate [REDACTED]

